### **2.3 Clinical assessment**

Parameters were assessed with the S390L Firefly WDR slit lamp (Shangai Mediworks Precision Instruments Co. Shangai, China) that includes a dry eye module designed to perform objective and non-invasive measures, which are analyzed by an artificial intelligence (AI) identification system (Mediview R3.0 software). To assess treatment efficacy, parameters were measured at baseline and the last visit. DED symptoms were assessed with the ocular surface disease index (OSDI) and symptom assessment in dry eye (SANDE) questionnaires. Ocular surface measurement was carried out by one examiner ([name]) in the following sequence to best preserve the integrity of the tear film to avoid affecting the test results: (1) tear film stability and volume; (2) ocular hyperemia; (3) ocular surface staining (OSS) and (4) meibomian gland analysis. Except for OSDI and SANDE questionnaires, which were collected per subject, all other clinical outcomes were collected per eye. To evaluate treatment safety, post-treatment adverse events were reported.

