#### **2.3.1 Tear film stability and volume**

Tear film stability was evaluated automatically by the AI identification system via detection of the first (F-NIBUT) and average noninvasive tear film break-up time (A-NIBUT) using a Placido disc. To assess the lipid layer grade (LLG), the lipid layer interferometric pattern was compared with the lipid layer thickness (LLT) grading scale template provided by the device, which has the following values: 1; LLT < 30 nm; 2, LLT of 30-60 nm; 3, LLT of 60-80 nm and 4, LLT >80 nm. Regarding tear volume, tear meniscus height (TMH) and tear meniscus area (TMA) were also automatically assessed by the AI identification system through focused image of the lower eyelids.

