### **2.3.5 Meibomian gland analysis**

Meibomian gland analysis was performed on the upper and lower eyelid using infrared light after everting the eyelids with a cotton swab. the AI identification system automatically analyzed the meibomian glands, obtaining the upper loss area Meibomian gland (U-LAMG) and lower loss area Meibomian gland (L-LAMG) with a value between 0% (no glandular dropout) and 100% (the highest level of glandular dropout), and upper meibomian gland dysfunction grade (U-MGD grade) and lower meibomian gland dysfunction grade (L-MGD grade), which have the following values: 0, no MGD; 1, mild MGD; 2, moderate MGD and 3, severe MGD.

Meibomian gland secretion was assessed by MGX. Fifteen glands on the lower eyelids were evaluated. For each gland, the secretion had the following scores: 0, no secretion; 1, inspissated/toothpaste consistency; 2, cloudy liquid secretion; and 3, clear liquid secretion. Then, three meibomian gland parameters were assessed: meibomian gland yielding secretion score (MGYSS) (range: 0-45), which was defined as the sum of the grades for all 15 glands, meibomian gland yielding clear secretion (MGYCS) (range: 0-15) and meibomian gland yielding liquid secretion (MGYLS) (range: 0-15).

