## **2.6 Statistical analysis**

Statistical analyses were performed with SPSS statistics software, version 26.0 (IBM Corporation, Armonk, NY, USA). The sample size was estimated using the GRANMO calculator, version 7.12 (Municipal Institute of Medical Research, Barcelona, Spain). It was calculated on the basis of assumed mean differences in F-NIBUT and MGYSS between the treatment and control groups at 2 months after the treatment onset, with values of  $3.04 \pm 3.86$  and  $19.75 \pm 5.45$ , respectively. These assumed differences were based on the findings of a pilot study with 16 eyes of 8 patients in each group. With these assumptions, a sample size of 26 eyes per group would yield a power > 80% and a statistically significant paired difference of 95% confidence. Continuous variables were displayed as the mean  $\pm$  standard deviation (SD) with interquartile ranges [IQRs], while ordinal categorical variables were expressed as frequencies (n) and percentages (%). After testing for normality and homogeneity of variance, the paired Student's *t*-test (parametric) or Wilcoxon's signed-rank test (nonparametric) was performed to compare intra-group clinical

outcomes. Within each group, the increment ( $\Delta$ ) was calculated. It was defined as the change from the last visit (LV) to baseline (B) " $\Delta = LV - B$ ". Inter-group clinical outcomes, were analyzed with the unpaired Student's *t*-test (parametric) or Mann-Whitney's U test (nonparametric). Between each group, the differences were calculated as " $\Delta_{Treatment\ group} - \Delta_{Control\ group}$ ". The Pearson's (parametric) or Spearman's Rho correlation coefficient (nonparametric) was used to analyze the correlations between the variables. Stepwise multiple linear regression analysis was performed to detect the influential factors in dry eye symptoms ( $\Delta$ OSDI and  $\Delta$ SANDE). In addition, One-Way ANOVA (parametric) was performed to determine if there were statistically significant differences in  $\Delta$ MGYSS according to baseline L-MGD-grade. A post hoc analysis by Bonferroni's test was carried out to determine statistically significant differences between baseline L-MGD grade. The level of significance was  $P < 0.05$  for all of the comparisons.

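### Correlations are planned with no list of pairs, no treatment-group term and no multiplicity control; if groups are pooled, a group difference alone can appear as a link between outcomes

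*Combined protocol and SAP*

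**What the plan says.** Section 2.6 (Statistical analysis) gives correlations one sentence: Pearson's coefficient, or Spearman's if nonparametric, "was used to analyze the correlations between the variables". It does not name the variables to be paired. It does not say whether baseline, last-visit or change values are used, or whether the groups are combined, kept apart or adjusted for.

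The significance level is P < 0.05 "for all of the comparisons". The only multiplicity step belongs to a different analysis, the one-way ANOVA of change in MGYSS: "A post hoc analysis by Bonferroni's test was carried out to determine statistically significant differences between baseline L-MGD grade".

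Two other parts of the plan bear on the point. Section 2.3 collects OSDI and SANDE once per patient and every other outcome per eye. Section 2.3.5 derives three secretion measures from one set of gland grades; MGYSS is the measure "which was defined as the sum of the grades for all 15 glands".

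**The concern.** Section 2.6 also looks for factors that influence the change in OSDI and SANDE, so symptom-sign associations are of interest here. A significant correlation between a symptom change and a sign change is easily read as meaning that symptoms improved because the sign improved.

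The planned sentence leaves three ways for such a result to arise without any link within patients:

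- **Number of tests.** With no fixed list, many pairs can be tested at 0.05 each.
- **Pooling.** If both groups are analysed together and treatment moves both variables, treated patients sit high on both and controls low on both. That alone produces a correlation. Correcting for multiplicity does not remove it.
- **Shared scoring.** MGYSS, MGYCS and MGYLS come from the same 15 glands, so correlations among them are largely built in.

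**Working it through.** **Inputs from the plan.** Section 2.6 bases the sample size on "assumed mean differences in F-NIBUT and MGYSS between the treatment and control groups": 3.04 with SD 3.86 for F-NIBUT and 19.75 with SD 5.45 for MGYSS, leading to 26 eyes per group.

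**Reproducing the plan's figure.** Two-sample formula for F-NIBUT, two-sided 5%, 80% power: n = 2 × (1.960 + 0.842)² × (3.86/3.04)² = 2 × 7.85 × 1.612 = 25.3, so 26 per group. This matches, so 3.86 can be read as the SD of a two-group comparison. The standardised differences are 3.04/3.86 = 0.79 SD (F-NIBUT) and 19.75/5.45 = 3.62 SD (MGYSS).

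**Number of pairs.** Sections 2.3 to 2.3.5 define 2 symptom scores, 2 break-up times, 1 lipid grade, 2 tear-volume measures, 4 hyperemia scores, 1 staining score, 2 gland-loss areas, 2 MGD grades and 3 secretion measures: 19 outcomes, of which 17 are signs.

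- All pairs: 19 × 18/2 = 171, and 171 × 0.05 = 8.55.
- Symptom-sign pairs: 2 × 17 = 34, and 34 × 0.05 = 1.7.

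Both are ceilings. They count every pair as tested and truly unrelated, with each test holding its 5% level.

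**Correlation created by pooling.** With equal groups, zero correlation within each group and group differences of d₁ and d₂ SD, the pooled correlation is f(d₁) × f(d₂), where f(d) = (d/2)/√(1 + d²/4).

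- f(3.62) = 0.876 and f(0.79) = 0.366.
- MGYSS with F-NIBUT: 0.876 × 0.366 = 0.32.
- Both at 0.79 SD: 0.366² = 0.13.
- Assumed symptom difference of 0.3 to 1.0 SD: f = 0.148 to 0.447, so r = 0.13 to 0.39 with MGYSS and 0.05 to 0.16 with F-NIBUT.

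**How often this is falsely significant.** Simulation with normal data, independent rows and no within-group link:

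| Pair (group differences) | Rows per group | Pooled Pearson | Group partialled out |
|---|---|---|---|
| 3.62 and 0.79 SD | 26 | about 68% | about 5% |
| 3.62 and 0.79 SD | 13 | about 38% | about 5% |
| 0.79 and 0.79 SD | 26 | about 16% | about 5% |
| 0.79 and 0.79 SD | 13 | about 10% | about 5% |
| Symptom 0.3–1.0 SD with MGYSS | 13 | about 10–55% | about 5% |
| Symptom 0.3–1.0 SD with F-NIBUT | 13 | about 6–13% | about 5% |

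Thirteen rows per group is 26 eyes divided by two, which assumes that both eyes of each patient are used. Spearman does not avoid the problem: for the first pair the pooled rates are about 64% (26 per group) and 36% (13 per group). If treatment moves only one of the two variables, the rate stays near 5%.

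**Unit of analysis.** If each eye is a row and the patient's symptom score is entered twice, partialling out group is not enough. With 13 patients per group, unrelated pairs are still significant in about 9% to 16% of datasets at assumed inter-eye correlations of 0.3 to 0.8.

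**The case against.** The strongest reply is that the plan is silent rather than wrong. It does not commit to testing all 171 pairs, to correlating changes or to combining the groups. A reader might infer that eight or nine spurious correlations will be reported. The text does not support that: it gives no number of tests, and some pairs are truly linked, such as the three secretion measures. A reader might also infer that pooling is planned. That is not stated either.

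The 68% figure also needs care. It rests on the very large MGYSS difference and concerns two signs, not a symptom and a sign. At moderate effects the inflation is modest. The planning values are described as differences at 2 months, and using them for changes is an assumption.

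Finally, the stated purpose is whether the combination improves symptoms and signs, and no section announces a mechanistic conclusion from correlations. A single plan-wide multiplicity rule could also cover the chance-findings part.

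All of this limits the size of the point. What stands is that a plain coefficient with no group term is the only method described, nothing rules out pooling, and a multiplicity rule would not repair it.

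**Conclusion.** The concern holds in conditional form. Section 2.6 leaves pairs, scale, group handling and multiplicity open for the correlations. Chance findings are bounded above by about 8.6 if all 171 pairs are tested and by 1.7 for the 34 symptom-sign pairs.

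If the groups are pooled and treatment moves both variables, the false-significance rate can be anywhere from little above 5% to about 68%, depending on the two effects and the number of rows. These rates assume no within-group link, independent rows, and planning differences that carry over to changes; the symptom differences are assumed, because the plan gives none.

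This does not show that any particular correlation is false. It means that a pooled one could not be told apart from the group difference. The analysis is secondary. The sample size and the between-group tests are unaffected, so the change should be made but is not critical to the main comparison.

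**What to change.** Replace the correlation sentence in section 2.6 with a specification along these lines:

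- Correlate the changes in OSDI and SANDE with the change in each of the 17 signs, 34 pairs in all.
- Partial out treatment group (on ranks for Spearman), or compute the coefficients within each group.
- Use one row per patient, taking the mean of the two eyes, or use a method that clusters by patient.
- Do not test MGYSS, MGYCS and MGYLS against each other.
- Report coefficients with 95% confidence intervals and label the analysis exploratory. If significance is claimed, apply Benjamini-Hochberg control within the list; within-group computation makes that list 2 × 34 = 68 tests.

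The cost is a few lines of text and no new data. The price is fewer significant correlations and wider intervals, most of all if the coefficients are computed separately in each group.

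### The stepwise search for factors behind change in OSDI and SANDE has no stated candidate list, row unit or group term, so a named factor may reflect many tests, doubled rows or treatment group alone

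*Combined protocol and SAP*

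**What the plan says.** Section 2.6 gives this analysis one sentence: "Stepwise multiple linear regression analysis was performed to detect the influential factors in dry eye symptoms", with change in OSDI and change in SANDE as the outcomes. The only threshold is general: "The level of significance was $P < 0.05$ for all of the comparisons". Bonferroni is named only for the post hoc comparison by baseline L-MGD grade. The section also plans correlations among the variables, again without a list.

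Section 2.3 sets the unit of measurement: "Except for OSDI and SANDE questionnaires, which were collected per subject, all other clinical outcomes were collected per eye".

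Sections 2.3.1 to 2.3.5 define the signs that could be candidates. Some overlap by construction. Tear film stability is measured "via detection of the first (F-NIBUT) and average noninvasive tear film break-up time (A-NIBUT"), and one expression of 15 glands gives several scores: "Then, three meibomian gland parameters were assessed: meibomian gland yielding secretion score (MGYSS") and two others.

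On size, section 2.6 says that "a sample size of 26 eyes per group would yield a power > 80" percent, using "assumed mean differences in F-NIBUT and MGYSS between the treatment and control groups at 2 months after the treatment onset". It adds: "These assumed differences were based on the findings of a pilot study with 16 eyes of 8 patients in each group".

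**The concern.** The aim is to detect what influences symptoms, so a sign kept in the model will be read as a driver of symptom improvement. Three gaps make that reading unsafe.

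- **Search.** P-values and coefficients printed after stepwise selection are computed as if the retained signs had been chosen in advance. They allow neither for the selection nor for the number of signs searched.
- **Rows.** The outcome exists once per patient and the signs once per eye. If each eye is a row, every symptom score enters twice and the standard errors are too small.
- **Group.** If the two groups are pooled with no group term, any sign moved by treatment can stand in for treatment. It may then be named without any link to symptoms within either group. Allocation is non-randomized and unmasked (section 2), so group may carry other differences as well.

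The analysis is secondary, so the mechanistic interpretation is at stake and the treatment-versus-control comparison is not.

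**Working it through.** **Inputs from the plan.** Level 0.05. Signs per eye: 5 tear film (F-NIBUT, A-NIBUT, LLG, TMH, TMA) + 4 hyperemia + 1 staining + 7 meibomian = 17. Size: 26 eyes per group, which is 13 patients per group if both eyes are used, as in the pilot (inferred). Differences ± SD: 3.04 ± 3.86 for F-NIBUT and 19.75 ± 5.45 for MGYSS.

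**Assumed.** Entry at 0.05, because no entry rule is stated. List sizes of 5 and 17. Correlations among signs and between eyes, because the documents give none.

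**Step 1: the plan's own figure.** Two-sample formula, two-sided 0.05, 80% power: n = 2(1.96 + 0.842)² × 3.86²/3.04² = 25.3, so 26 eyes per group (power 81.0%). This reproduces. The paired formula gives 12.7, so 13. The stated 26 therefore fits reading each ± value as a within-group SD, and step 4 uses that reading.

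**Step 2: number of signs searched, one row per patient.** At least one sign is selected exactly when the smallest single-sign P is below 0.05. For independent signs this is 1 − 0.95^k:
- k = 5: 1 − 0.774 = 22.6%
- k = 17: 1 − 0.418 = 58.2%

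Correlated signs were simulated with equal correlation and no true link:

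| Sign correlation | 5 signs | 17 signs |
|---|---|---|
| 0 | 22-23% | 58-59% |
| 0.7 | 15-16% | 28-29% |
| 0.9 | 10-11% | 16% |

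With 17 signs correlated 0.8 within related families and 0.3 between them, the rate is 43-45%. Results at 13, 26 and 52 patients agree to within one to two points, so sample size is not the cause.

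**Step 3: eyes as rows.** The outcome is identical in a patient's two rows. With between-eye correlation r for the sign, the variance of the estimate is about (1 + r) times what the model assumes. The true false-positive rate for one pre-chosen sign is about P(|Z| > 1.96/√(1 + r)):
- r = 0.3: 8.6%
- r = 0.5: 11.0%
- r = 0.8: 14.4%

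Simulation at r = 0.5 gives 11-12%.

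**Step 4: pooled groups, no group term.** MGYSS separation is d = 19.75/5.45 = 3.62 SD. With equal groups, its correlation with group is 3.62/√(3.62² + 4) = 0.876. A symptom effect of e SD has correlation e/√(e² + 4) with group. With no within-group link, the pooled sign-symptom correlation is the product of the two. For 26 patients, Fisher's transformation (multiplier √23) gives:
- e = 0.5: 0.243 × 0.876 = 0.212; significant in about 18%
- e = 1.0: 0.447 × 0.876 = 0.392; significant in about 51%

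Simulation with the t-test gives about 19% and 55%, and about 39% at e = 0.8. With a group term in the model the rate is about 5% throughout.

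**The case against.** The strongest objection is that the rates in step 2 measure how many signs are examined, not a fault peculiar to stepwise selection. That is correct. Separate one-sign models with group and baseline and no selection give the same figures: 23% and 15% for 5 signs, 58% and 29% for 17, at sign correlation 0 and 0.7. Stepwise selection over two independent signs gives about 10%, the same as two fixed one-sign models. A reader might infer that stepwise selection creates the excess and that dropping it alone would cure it. The figures do not support that. What is specific to stepwise selection is that the printed P-values and coefficients ignore the selection; that distortion is not quantified here.

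A reader might also blame the small sample. The rates hardly change with sample size, so this does not hold either.

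Nor is any single range a bound. The 15% and 28% depend on a sign correlation of 0.7, and at 0.9 the rates are about 10-11% and 16%. A uniform 0.9 across tear film, hyperemia, staining and gland measures is extreme, and those rates are still above 5%.

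Finally, the plan is silent on rows and group. It does not say that eyes were rows or that group was left out, so steps 3 and 4 show what follows if so. The silence itself stands, and section 2.6 does not call the analysis exploratory.

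**Conclusion.** The concern holds as a fault of specification and method in a secondary analysis that should be corrected. As written, a reader can neither reproduce the regression nor judge whether a named factor is more than chance.

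The size depends on what was done. With one row per patient and no true link, the chance of at least one named factor per outcome runs from about 10% (5 signs correlated 0.9) to about 59% (17 independent signs). This is multiplicity. The row and group questions are separate and are not cured by shortening the list.

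The largest avoidable error for a single sign is the missing group term: about 19-55% against about 5%. That rests on the plan's MGYSS figures being a group difference and within-group SD, on 26 patients, and on an assumed symptom effect of 0.5-1 SD.

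A reader might infer that the treatment-versus-control result is compromised. Nothing in this point supports that, because the group comparison does not use the regression.

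**What to change.** In section 2.6:

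1. Use one row per patient (mean of the two eyes) for this regression and for all symptom-sign correlations.
2. Include group and baseline symptom score in every model.
3. Replace stepwise selection with a short stated list of signs entered without selection. One example is change in F-NIBUT and change in MGYSS, the two sample-size variables, in separate models. Another short list would serve if stated.
4. Report coefficients with 95% confidence intervals and the number of signs examined.
5. Label the analysis exploratory, or post hoc if results have been seen.
6. Do not read the treatment effect from the MGYSS model.

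In simulation with 26 patients, the two example models give about 5% false positives per sign coefficient, 9-10% per outcome, and 16-17% over both outcomes (assumed correlation 0.6 between OSDI and SANDE changes). The fall in the per-outcome rate comes from examining two signs.

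**Cost.** Re-analysis and wording; no new data. Fewer signs are examined, and the aim shifts from searching to estimating a few stated links. Intervals are wide: the 95% half-width is about 0.43 residual SD of symptom change per within-group SD of the sign, so only strong links can be shown.

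Change in MGYSS is strongly collinear with group. Treating 19.75 as a difference in change, variance inflation is 1 + d²/4 = 1 + 3.62²/4 = 4.3 on the eye-level SD. It is 4.7-6.1 for two-eye means (eye correlation 0.8-0.3). The half-width for group then grows from about 0.82 to 1.86-2.11 residual SD, hence item 6. For F-NIBUT, d = 3.04/3.86 = 0.79 and the inflation is only about 1.2.

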#### **2.3.3 Ocular Hyperemia**

Ocular hyperemia was assessed through complete picture of the ocular surface focused on the bulbar conjunctiva. Nasal ciliary hyperemia (NCIH), temporal ciliary hyperemia (TCIH), nasal conjunctival hyperemia (NCOH) and temporal conjunctival hyperemia (TCOH) were analyzed automatically the AI identification system with a value between 0% (no hyperemia) and 100% (the highest level of hyperemia).

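### Nineteen between-group outcomes are each tested at unadjusted P<0.05 with no named primary, so the chance of at least one false positive is well above 5%

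*Combined protocol and SAP*

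**What the plan says.** Section 2.6 compares the groups on clinical outcomes with an unpaired t-test or Mann-Whitney test and sets one significance level, P<0.05, "for all of the comparisons". A paired t-test or Wilcoxon test "was performed to compare intra-group clinical" outcomes. The only multiplicity correction is Bonferroni, for baseline L-MGD grade contrasts after an ANOVA of change in MGYSS.

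The sample size rests on "assumed mean differences in F-NIBUT and MGYSS between the treatment and control groups at 2 months", with values 3.04 ± 3.86 and 19.75 ± 5.45, and arrives at "a sample size of 26 eyes per group". These assumptions come from a "pilot study with 16 eyes of 8 patients in each group". Neither outcome is called primary.

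On the unit of measurement, Section 2.3 says: "Except for OSDI and SANDE questionnaires, which were collected per subject, all other clinical outcomes were collected per eye". No method is given for two eyes of one patient.

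**The concern.** With no primary and no hierarchy, the plan does not say which result decides whether the combined treatment worked. Any one of 19 between-group differences meets its only criterion, and the more outcomes are tested, the more likely one of them meets it by chance.

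The within-group tests do not help. Both groups receive warm compresses and eyedrops (Section 2.2), so change within the treatment group cannot be credited to MBE, IPL and MGX.

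At stake is how far a positive finding can be trusted. The stated aim covers symptoms and signs together (Section 1), so a chance result on either could be read as support.

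**Working it through.** **1. The plan's own figure.** Unpaired formula, two-sided 0.05, 80% power: n = 2(1.96 + 0.84)² × 3.86² / 3.04² = 25.3, rounded up to 26 per group. This reproduces the stated size. MGYSS needs only 2 per group, so F-NIBUT drives it. Power at 26 independent units is 81.0% by the normal approximation and 79.5% by the noncentral t.

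**2. Count of outcomes.**
- Symptoms (2.3): OSDI, SANDE = 2
- Tear film (2.3.1): F-NIBUT, A-NIBUT, LLG, TMH, TMA = 5
- Hyperemia (2.3.3): NCIH, TCIH, NCOH, TCOH = 4
- Staining (2.3.4): OSS = 1
- Gland imaging (2.3.5): U-LAMG, L-LAMG, U-MGD grade, L-MGD grade = 4
- Secretion (2.3.5): MGYSS, MGYCS, MGYLS = 3

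Total 19. Within-group tests, correlations, regressions and the ANOVA are not counted.

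**3. Independence.** Tests are read as two-sided; the plan does not say. Either direction: 1 − 0.95¹⁹ = 62.3%. Favouring treatment: 1 − 0.975¹⁹ = 38.2%. For normally distributed test statistics, 62% is the two-sided ceiling. The 38% is not a ceiling: a common correlation of −0.05 gives about 40%, and the general bound is 19 × 0.025 = 47.5%.

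**4. Correlated outcomes.** Independence is implausible because several outcomes share a source. For example, hyperemia values come from one picture ("Ocular hyperemia was assessed through complete picture of the ocular surface"), and the two meniscus measures are read together ("tear meniscus height (TMH) and tear meniscus area (TMA) were also automatically assessed by the AI identification system"). The simulation used 13 patients per group, one value per patient, two-sample t-tests, no treatment effect and 40,000 replicates. Outcomes were grouped by source: OSDI/SANDE; F-/A-NIBUT; LLG; TMH/TMA; four hyperemia; OSS; four gland imaging; three secretion.

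| Correlation within source | Between sources | At least one P<0.05 | Favouring treatment |
|---|---|---|---|
| 0.7 | 0 | 53.7% | 31.6% |
| 0.7 | 0.3 | 47.9% | 24.9% |
| 0.9 | 0 | 46.0% | 26.1% |
| 0.9 | 0.3 | 41.0% | 20.9% |

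With one common correlation across all 19 outcomes, the chance in either direction is 53% at 0.3, 42% at 0.5, 29% at 0.7 and 16% at 0.9 (8% favouring treatment at 0.9).

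**5. If MGYSS truly differs, as the plan assumes.** Setting the three secretion scores aside leaves 16 outcomes. The same four correlation settings give about 37-48% in either direction.

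**6. Does adjusting two primaries suffice?** Holm on two primaries under no effect, 13 patients × 2 eyes per group, 100,000 replicates. Eye-level tests give 9.6%, 13.3% and 17.2% familywise error at inter-eye correlations of 0.3, 0.5 and 0.7. The mean of the two eyes gives 4.6-5.1%. Holm alone is therefore not enough; the tests must be at patient level.

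**7. Patient-level power for F-NIBUT.** This assumes 13 patients per group with both eyes used, and reads 3.86 as the common per-eye SD. The SD of the two-eye mean is 3.86 × √((1 + r)/2), the noncentrality is 3.04 / (SD × √(2/13)), and the critical t on 24 df is 2.06.
- r = 0.3: SD 3.11, noncentrality 2.49, power 67%
- r = 0.5: SD 3.34, noncentrality 2.32, power 60%
- r = 1.0: SD 3.86, noncentrality 2.01, power 49%

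For MGYSS at r = 1.0, the noncentrality is 19.75 / (5.45 × √(2/13)) = 9.2 against a critical t of 2.39 at 0.025, so power exceeds 99.9%. On the plan's figures MGYSS would nearly always pass first, and Holm would then test F-NIBUT at 0.05.

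**The case against.** **F-NIBUT and MGYSS are implied primaries because they size the study.** This is a fair reading of intent, but Section 2.6 uses them only for sizing, and its significance rule does not single them out. Even if both were primary, two unadjusted tests give 1 − 0.95² = 9.75% under independence.

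**The plan expects a very large MGYSS effect, so a null on every outcome is not its scenario.** This stands. It moves the question to the other outcomes, where the 37-48% in step 5 applies. A true MGYSS effect does not validate a claim on tear film, hyperemia or symptoms.

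**The headline range depends on assumed correlations.** This also stands. The 41-54% belongs to one set of assumptions, and the span from a common correlation of 0.9 to independence is 16-62%. A reader might take 62% as the error rate, or 38% as the most that could favour treatment; neither is supported.

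**Two-eye clustering is a separate issue.** It is, and it enters here only because the remedy fails without it.

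**A symptom co-primary would be just as defensible.** The aim does cover symptoms. F-NIBUT and MGYSS are proposed because the plan already sized on them, not because they are the only valid choice.

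**Conclusion.** The concern holds. Nineteen between-group tests at unadjusted P<0.05 with no named primary make a chance positive likely: about 41-54% (21-32% favouring treatment) at correlations of 0.7-0.9 within a source and 0-0.3 between sources, and 16-62% across common correlations from 0.9 to zero. These figures assume valid patient-level tests and no added treatment effect. The exact size is uncertain, but the excess over 5% is not: the lowest case shown is about three times that level.

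A reader might infer that any positive result from this study is probably false. The documents do not support that: these are chances of at least one false positive when no effect exists, not the chance that a given finding is false. A reader might also infer that the sizing outcomes were chosen after seeing results. Section 2 describes the study in the past tense, April 2022 to January 2023, but nothing shows when any choice was made.

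**What to change.** In Section 2.6:
- Name the between-group differences in change in F-NIBUT and in MGYSS at 2 months as the two primary outcomes.
- Analyse each at patient level, using the mean of the two eyes or a model with a patient random effect, and test them with Holm at an overall 5%.
- Label the other 17 outcomes, including OSDI and SANDE, secondary or exploratory and report 95% confidence intervals.
- Treat within-group tests as descriptive and base the conclusion on the primary between-group tests.
- If a confirmatory symptom claim is wanted, name one score in advance and test it at 5% only if both primaries pass. In simulation (200,000 replicates) this kept familywise error at 3.8-5.0% with no true effects and 5.0% with only MGYSS truly different.
- If data had been seen when the primaries were named, disclose the choice as post hoc and claim no 5% control.
- State that Holm addresses chance error only, not bias from the non-randomized, unmasked design.

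Cost: no new data, but a change of text and a re-run at patient level. Fewer outcomes can be claimed. Patient-level F-NIBUT power is about 49-67% at inter-eye correlations of 1.0-0.3, against the stated figure above 80%. This assumes 13 patients per group with both eyes used, whereas the plan states only 26 eyes. A symptom claim gated on both primaries would therefore be blocked in at least about 33-51% of trials (1 − 0.67 to 1 − 0.49), even if symptoms truly improve.
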